#### 2.4.3 Handling of Missing Values/ Discontinuations

For the primary analysis, subjects are considered responders if they meet response criteria for the primary endpoint on or before month 24 (week 104). Any subject who discontinues treatment prematurely before meeting such criterion is counted as non-responder. Any subjects with unknown or missing SF (no viable post-baseline SF assessment during the study) by 24 months will also be counted as non-responder.

# 2.5 Analysis Supporting Secondary Objectives

The key secondary objective for this study is to characterize the ocular safety of deferasirox FCT and phlebotomy over 24 months.

#### 2.5.1 Key Secondary Endpoint

The key secondary endpoint is the Ocular Adverse Event as defined by AESI of "Lens disorders, retinal disorders and optic neuritis". This analysis will be carried out in the Safety Set.

#### 2.5.2 Statistical Hypothesis, Model, and Method of Analysis

To characterize long-term ocular safety, the incidence of treatment-emergent ocular AEs (new or worsening from baseline) will be summarized (along with two-sided exact binomial 95% CIs [Clopper and Pearson, 1934]) by preferred term, overall and by severity, type of AE (e.g. serious, leading to study drug discontinuation, requiring dose adjustment or/and interruption), and relation to study treatment.

Treatment-emergent AEs are defined as AEs started during on-treatment period: from the day of the first dose of study medication or the first phlebotomy to 30 days after the last dose of study medication or last phlebotomy.

All ocular AEs included under "Lens disorders, retinal disorders and optic neuritis" Adverse Event of Special Interest (AESI, listed in the compound case retrieval strategy) will be reported.

Novartis	Confidential	Page 22 of 36
SAP Amendment 1		Study No. CICL670F2203

The above analysis will also be repeated for the overall period (on-treatment & post-treatment).

The analyses will be descriptive. No formal hypothesis testing is planned for this key secondary objective.

A listing of Ocular AEs will also be generated, and post-treatment events will be flagged.

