10.8 Sample size calculation

The primary objective of the study is to estimate response rates and therefore the sample size is not based on power calculations. Sample size calculations were performed for the deferasirox FCT and phlebotomy arms to estimate the response rate (RR) with reasonable accuracy (half-width of 95% confidence interval).

Based on the Exjade study ICL670A2202, the patient dropout rate at month 6 (core study) is 24% and 12% at month 12 (optional extension phase). Assuming decreasing dropout rate over time and expected better patient compliance with deferasirox FCT formulation, a sample size of 100 patients in the FCT arm is expected to have at least 60 patients followed for 24 months to fulfil the FDA post-marketing requirement with regard to the ocular toxicity assessment in patients receiving deferasirox.

With a sample size of 100 on deferasirox FCT and 50 patients on phlebotomy, the projected half-widths of the 2-sided 95% confidence interval assuming various response rates are displayed in Table 10-3. The 95% confidence interval half-width extends at most to 0.096 and 0.136 in the deferasirox FCT and phlebotomy arms, respectively.

phiebotomy arms			
Response rate (RR)	Half-width of the 95% CI for deferasirox FCT N=100	Half-width of the 95% CI for phlebotomy N=50	
0.60	0.096	0.136	
0.65	0.093	0.132	
0.70	0.090	0.127	
0.75	0.085	0.120	
0.80	0.078	0.111	
0.85	0.070	0.099	
0.90	0.059	0.083	

Table 10-3Half-width of 95% CI of response rates in deferasirox FCT and
phlebotomy arms

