#### **General Analysis Conventions**

**Pooling of centers:** Unless specified otherwise, data from all study centers will be pooled for the analysis. Due to expected small number of subjects enrolled at centers, no center effect will be assessed.

**Qualitative/categorical data** (e.g., sex, race) will be summarized by frequency counts and percentages. Percentages will be calculated using the number of subjects in the relevant treatment arm as the denominator.

**Continuous data** (e.g., age, body weight) will be summarized using appropriate descriptive statistics (i.e. mean, standard deviation, median, minimum, and maximum) by treatment arm. Lower and upper quartiles will also be presented when applicable.

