#### **On-treatment Period**

The overall observation period (for both Deferasirox and Phlebotomy) will be divided into three mutually exclusive segments:

- Pre-treatment period: from day of subject's first informed consent to the day before first administration of study treatment;
- On-treatment period: from day of first administration of study treatment to 30 days after last administration of study treatment;
- Post-treatment period: starting at day 30+1 after last administration of study treatment to end of study.

Safety summaries (tables, figures) include only data from the on-treatment period with the exception of baseline data which will also be summarized where appropriate (e.g. change from baseline summaries). For additional details refer to specific section – Section 2.6.3 details on AEs and Section 5.3.2 on Ocular assessments.

However, all safety data (including those from the post-treatment period) will be listed and those collected during the pre-treatment and post-treatment period will be flagged.

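### The key secondary ocular AE incidence is a crude proportion over unequal risk windows, so it understates 24-month risk and can distort the arm comparison in a direction the plan does not settle

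*SAP*

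**What the plan says.** The key secondary objective in SAP 2.5 is to "characterize the ocular safety of deferasirox FCT and phlebotomy over 24 months". SAP 2.5.1 defines the endpoint through the AESI group of lens disorders, retinal disorders and optic neuritis, analysed in the Safety Set. SAP 2.5.2 states that "the incidence of treatment-emergent ocular AEs (new or worsening from baseline) will be summarized (along with two-sided exact binomial 95% CIs", broken down by preferred term, severity, type of AE and relation to treatment.

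Two other rules fix the estimator. The general conventions in SAP 2.1 state: "Percentages will be calculated using the number of subjects in the relevant treatment arm as the denominator". The treatment-emergent window in SAP 2.5.2 runs from first treatment "to 30 days after the last dose of study medication or last phlebotomy", so its length differs between subjects.

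SAP 2.5.2 repeats the same analysis for the on-treatment and post-treatment periods combined. It is descriptive, without a test. SAP 2.3.1 summarises duration of exposure for each arm separately. Kaplan-Meier estimation is planned only for time to response (SAP 2.6.1).

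On dropout, Protocol 10.8 (repeated in SAP 3) reports from an earlier deferasirox study that "the patient dropout rate at month 6 (core study) is 24% and 12% at month 12 (optional extension phase". It assumes that dropout slows over time and that compliance improves with the film-coated tablet, and expects 60 or more of the 100 deferasirox patients to be followed to month 24. Neither document gives a dropout rate for phlebotomy.

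**The concern.** A binomial proportion treats every subject as having had the same chance to show an event. Here they have not: the window closes shortly after treatment ends, and the plan itself allows for up to about 40 of 100 deferasirox subjects not reaching month 24. Subjects who leave early without an event stay in the denominator as if they had been event-free for the whole two years. The proportion then estimates the chance of an ocular AE before leaving treatment, which is lower than the 24-month risk the objective names. The exact interval is built around the same quantity, so it does not repair the shortfall.

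This matters because the study serves a post-marketing requirement on two-year ocular safety (Protocol 2.1). With no hypothesis test, the estimate is the result. If follow-up differs between arms, the two proportions are also not comparable, even at identical hazards.

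**Working it through.** **Inputs from the documents.** Arm sizes 100 and 50; historical deferasirox losses of 24% and 12% in the first two half-years; 60 or more of 100 expected at month 24 (Protocol 10.8); ocular disturbances below 1% in earlier studies (Protocol 2.6).

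**Assumptions.** Second-year deferasirox losses of 6% and 3% per half-year; all phlebotomy losses; a true 24-month risk R; a constant ocular hazard; dropout unrelated to ocular risk. The 30-day tail is left out at first.

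**The plan's own figure.** Month 12: 100 × 0.76 × 0.88 = 66.9. Month 24: 66.9 × 0.94 × 0.97 = 61.0, in line with the stated 60. Losses of 6% and 6% give 59.1. Continuing at 12% per half-year gives 51.8, which does not fit.

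**Formula.** With time in years, h = −ln(1 − R)/2. For half-year j with loss d_j, k_j = −ln(1 − d_j)/0.5. With S the proportion still followed at the start of the interval and t its start time, the interval adds S × exp(−h·t) × h/(h + k_j) × [1 − exp(−0.5(h + k_j))]. The expected crude proportion is the sum over four half-years.

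**Deferasirox at 24/12/6/3%, R = 10%.** h = 0.0527. The intervals add 2.28 + 1.81 + 1.60 + 1.49 = 7.17%. The ratio to the true risk is 7.17/10 = 0.72, about 28% too low. Mean follow-up is 5.25 + 4.28 + 3.89 + 3.72 = 17.1 of 24 months, and 17.1/24 = 0.71 agrees.

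| True 24-month risk | Crude, 24/12/6/3% | Crude, half the dropout (12/6/3/1.5%) |
|---|---|---|
| 1% | 0.71% | 0.85% |
| 5% | 3.6% | 4.3% |
| 10% | 7.2% | 8.5% |
| 20% | 14.4% | 17.1% |

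The relative shortfall is about 28% and 15%, nearly independent of R. No phlebotomy figure enters. Adding a one-month tail gives 7.6% at R = 10%, against 10.4% for complete follow-up with the same tail: a ratio of 0.73.

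**Between arms, equal hazards, R = 10%.** Phlebotomy loss is spread at a constant rate. Each ratio is deferasirox over phlebotomy, for the two deferasirox dropout patterns above.

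| Total phlebotomy loss | Phlebotomy crude | Ratio, deferasirox 24/12/6/3% | Ratio, deferasirox at half |
|---|---|---|---|
| 0% | 10.0% | 0.72 | 0.85 |
| 20% | 9.0% | 0.80 | 0.95 |
| 39% | 7.9% | 0.90 | 1.08 |
| 50% | 7.3% | 0.99 | 1.17 |
| 60% | 6.6% | 1.09 | 1.29 |

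With deferasirox at 24/12/6/3%, the ratio crosses 1 at about 52% phlebotomy loss. If no phlebotomy subject drops out but the window closes 6 or 8 months early because procedures stop at target ferritin, the ratio is 0.94 or 1.06.

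**After the change.** Under the same assumptions, expected events divided by expected time at risk equal h in each arm, and Kaplan-Meier targets 10% at month 24 in each. The ratio is 1.00 whatever each arm's dropout.

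**The case against.** The strongest reply has four parts.

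*The plan already shows unequal follow-up.* The analysis is repeated for the overall period, exposure is summarised for both arms, and swimmer plots set ocular assessments against dosing (SAP 2.6.2). A careful reader would see the imbalance. This stands in part, but the repeat is still a crude proportion. Post-treatment ocular follow-up is voluntary and needs at least six months of assessments (Protocol 4.1.1), so it misses those who leave in the half-year with the highest cited loss. Routine AE monitoring need only run 30 days, or five half-lives if longer, after the last dose (Protocol 8.1.1). Exposure runs from first to last treatment and is never tied to ocular events.

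*The dropout figures are historical.* This stands: the plan expects better compliance with the film-coated tablet. Halving the rates still leaves a shortfall of about 15%.

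*The absolute effect is small and nothing is tested.* This stands. At a 1% risk the error is about 0.3 per 100. Even at 10%, an observed 7/100 has an exact interval of 2.9% to 13.9%, which contains the true value.

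*The alternatives have weaknesses of their own.* This stands too; they are listed with the fix.

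A reader might go further and infer that deferasirox, as the arm with more dropout, is made to look safer. The documents do not support that. They give no phlebotomy rate, Protocol 2.1 remarks that phlebotomy compliance may decline, and target-driven interruption can shorten the window in either arm.

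**Conclusion.** The planned estimator does not match an objective framed over 24 months. It understates 24-month ocular risk by about 28% in relative terms at the historical dropout completed with assumed 6% and 3% second-year losses, and by about 15% at half that dropout. Both figures assume a constant hazard and non-informative dropout; neither needs a phlebotomy assumption. The arm comparison can be distorted either way: in the scenarios at the historical dropout the ratio runs from 0.72 to 1.09 at equal hazards, and it rises further if deferasirox dropout is lower. The plan's figures do not say where in that range the trial will fall.

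The practical weight is modest. At the cited ocular frequency the absolute error is about 0.7 against 1.0 per 100, and the analysis is descriptive. This is a cheap improvement to the headline safety estimate, not a flaw that invalidates the study.

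**What to change.** In SAP 2.5.2, for the ocular AE group, by arm and for both the on-treatment and the overall period, add:

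- the exposure-adjusted rate per 100 patient-years with an exact Poisson 95% CI, time at risk running from first treatment to the first ocular AE or the end of that subject's observation in the period;
- the cumulative incidence at month 24 with a 95% CI, by Kaplan-Meier, or by Aalen-Johansen with death as the competing event. Discontinuation should be censored: treating it as a competing event would bring back essentially the crude proportion.

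Keep the crude proportion as a count, and base any statement about 24 months on the cumulative incidence.

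The SAP should state the limits. Time at risk includes off-drug interruptions, which can dilute the deferasirox rate. Censoring may be informative, because ocular findings can prompt interruption (Protocol Table 6-2). Scheduled eye examinations are about six months apart, so onset dates of events found there are coarse. In the overall period, AE capture beyond the 30-day follow-up is incomplete.

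The cost is SAP wording and some programming. AE onset and treatment dates are already collected, so no new data are needed.

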# 2.6 Analysis of Secondary Efficacy Objective

The secondary efficacy objective is to assess the first time to response of achieving  $SF \le 100 \mu g/L$  between the defensirox and phlebotomy treatment arms.

#### 2.6.1 Secondary Efficacy Endpoint

The secondary efficacy endpoint of the study is the time from the date of randomization to the date of the first time the SF is achieving a value  $\leq 100 \ \mu g/L$  on or before month 24 (week 104), defined as Time To Response (TTR). This analysis will be carried out in the FAS.

TTR (in months) will be listed and summarized by treatment arm. The distribution of time to response will be estimated using the Kaplan-Meier method and the median time to response will be presented along with 95% confidence interval only if a sufficient number of responses is observed.

No inferential analysis that compares time to response between the two treatment arms will be performed.

Subjects who do not achieve SF  $\leq 100 \ \mu g/L$  will be censored as follows:

- at the last serum ferritin assessment date on or before month 24 (week 104),
- at the day of randomization if a subject does not have any post-baseline serum ferritin value,
- at the death date

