10.4.3 Handling of missing values/censoring/discontinuations

For the primary analysis, patients are considered responders if they meet response criteria for the primary endpoint on or before month 24. Any patient who discontinues prematurely before meeting such criterion will be considered a non-responder.

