10.5.2 Secondary efficacy objective(s)

The secondary efficacy objective is time to first response of achieving $SF \le 100 \ \mu g/L$. For this analysis, the following censoring rule will be applied:

For patients who did not achieve a response, they will be censored at the earliest of the following dates:

- Death or discontinuation date due to any reason
- Last SF assessment.

Kaplan-Meier estimates will be presented. Median time to response (as well as 25th and 75th percentiles) will be presented along with 95% confidence intervals for the two arms.

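### Time to response censors patients whom the primary analysis counts as non-responders, so its curve and median will look more favourable than the primary rate; the SAP's censoring dates are also unranked

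*SAP*

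**What the plan says.** **Primary endpoint.** Response is SF ≤ 100 µg/L at any time on or before month 24, analysed in the Full Analysis Set (FAS). SAP 2.4.3 says: "Any subject who discontinues treatment prematurely before meeting such criterion is counted as non-responder". Protocol 10.4.3 has the same rule: "Any patient who discontinues prematurely before meeting such criterion will be considered a non-responder". SAP 2.4.3 also counts patients with no usable post-baseline SF as non-responders.

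**Time to response.** SAP 2.6.1 uses the same event, the same week-104 limit and the FAS, with time counted from randomisation. It adds: "The distribution of time to response will be estimated using the Kaplan-Meier method".

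**Censoring dates.** Protocol 10.5.2 has one ordered rule: "For patients who did not achieve a response, they will be censored at the earliest of the following dates". The dates are "Death or discontinuation date due to any reason" and the last SF assessment. SAP 2.6.1 instead lists three bullets: the last SF on or before week 104, the day of randomisation if there is no post-baseline SF, and the death date. It does not say which date governs when two apply, and the discontinuation date is absent.

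**Outputs.** Protocol 10.5.2: "Median time to response (as well as 25th and 75th percentiles) will be presented along with 95% confidence intervals for the two arms". SAP 2.6.1 names only the median with its interval, and only if there are enough responses, a threshold it does not define.

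**Declared changes.** SAP section 4 lists COVID-19 analyses and the ocular windows. It does not mention time to response.

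**The concern.** The two efficacy results share an event, a horizon and a population but treat a pre-response discontinuer in opposite ways. In the primary, that patient stays in the denominator as a failure. In Kaplan-Meier, the patient leaves the risk set, and the estimate proceeds as if he or she would have gone on to respond at the same rate as those still under observation. Whenever at least one patient in an arm is censored before a later response in that arm, one minus the Kaplan-Meier estimate at month 24 exceeds the primary rate, and the median is never later than it would be with discontinuers kept as failures.

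No test is planned, so the estimates are themselves the efficacy result. A report could give a median time to response in an arm where fewer than half the patients count as responders, with nothing to tell the reader that the two results answer different questions.

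The censoring dates are a second, smaller matter. A non-responder with SF measurements who later dies satisfies two SAP bullets with two different dates, so two programmers could build different datasets from the same text.

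**Working it through.** **The plan's own figures.** Table 10-3 of the protocol gives a largest 95% half-width of 0.096 for deferasirox (N = 100) and 0.136 for phlebotomy (N = 50), at a response rate of 0.60. These reproduce with the normal approximation: 1.96 × √(0.60 × 0.40/100) = 0.0960 and 1.96 × √(0.60 × 0.40/50) = 0.1358. They serve below as a yardstick. The documents give no figure for the gap itself, so it has to be modelled.

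**Inputs.** Protocol 10.8 cites dropout of 24% at month 6 and 12% at month 12 from an earlier study of the other formulation. It expects at least 60 of 100 deferasirox patients to be followed for 24 months.

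**Assumptions.** The response hazard λ is constant and dropout is independent of response. The 12% is read as a share of those remaining at month 6. Two dropout patterns are used:

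- 24, 12, 6 and 3% per six months. The last two values are assumed, continuing the decline. Retention is 0.76 × 0.88 × 0.94 × 0.97 = 0.610.
- 5% in each six months, also assumed. Retention is 0.95⁴ = 0.815.

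**Formulas.** For six-month period i with dropout dᵢ:

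- dropout hazard: δᵢ = −ln(1 − dᵢ)/6 per month
- responders added: Sᵢ × λ/(λ + δᵢ) × [1 − exp(−6(λ + δᵢ))]
- still at risk: Sᵢ₊₁ = Sᵢ × exp(−6(λ + δᵢ)), with S₁ = 1
- primary rate = sum of responders added over the four periods
- Kaplan-Meier response at month 24 = 1 − exp(−24λ)

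**Worked case 1: primary rate 50%, dropout 24/12/6/3%.** The dropout hazards are 0.0457, 0.0213, 0.0103 and 0.0051. Solving for λ gives 0.0462. Responders added are 0.213 + 0.131 + 0.090 + 0.065 = 0.50 (rounded). Kaplan-Meier gives 1 − exp(−24 × 0.0462) = 0.67.

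**Worked case 2: primary rate 50%, dropout 5% per six months.** δ = 0.00855 and λ = 0.03288. The primary rate is 0.03288/0.04143 × [1 − exp(−24 × 0.04143)] = 0.50. Kaplan-Meier gives 1 − exp(−24 × 0.03288) = 0.546.

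| Dropout per 6 months | Retained at month 24 | Primary rate | Kaplan-Meier, month 24 | Gap (points) |
|---|---|---|---|---|
| 24, 12, 6, 3% | 61% | 50% | 67% | 17 |
| 24, 12, 6, 3% | 61% | 58% | 77% | 19 |
| 24, 12, 6, 3% | 61% | 70% | 90% | 20 |
| 5% each | 81% | 50% | 55% | 5 |
| 5% each | 81% | 58% | 63% | 5 |
| 5% each | 81% | 70% | 76% | 6 |

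The timing of dropout matters as well as its total. With a 40% loss spread evenly over 24 months, Kaplan-Meier values of 60–90% pair with primary rates of 48.8–76.9%, a gap of 11–13 points.

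**Median.** Take a primary rate of 58% with the early-weighted pattern (λ = 0.06065). The Kaplan-Meier median is ln 2/0.06065 = 11.4 months. With discontinuers kept as failures, half the arm has responded only at 16.8 months. At 5% per six months (λ = 0.04153) the two medians are 16.7 and 18.4 months.

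**Censoring dates.** SF is scheduled only up to the end-of-treatment visit (protocol 7.2.1.1 and Table 7-1), and post-treatment follow-up schedules eye examinations. A discontinuer's last SF is therefore normally on or before about that visit, and the protocol's rule usually resolves to the last SF, which is also the SAP's first bullet. The unresolved case is the non-responder who dies.

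**The case against.** The strongest defence is that Kaplan-Meier with censoring is the protocol's own method, so the SAP is following it. The primary asks what share of randomised patients responded; time to response asks when response occurs. Both are descriptive, so error rates, sample size and the primary result are untouched. All of that stands.

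Four stronger readings are tempting, and the documents do not support them.

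- A reader might infer that the Kaplan-Meier curve is shown to be biased by informative censoring. The calculation assumes independent dropout. Under that assumption Kaplan-Meier correctly estimates response in the absence of discontinuation, so the gap separates two quantities and does not measure bias. Dropout related to prognosis is plausible but is neither documented nor modelled here.
- A reader might infer that the report will carry two competing month-24 response rates. SAP 2.6.1 plans the distribution and a median, with no month-24 Kaplan-Meier rate. Such a figure can only be read off the curve.
- A reader might infer that the display favours one arm. Without a phlebotomy dropout figure, neither the direction nor the size of a between-arm effect can be given.
- A reader might infer that losing the discontinuation date alters the results. Given when SF is scheduled, it will usually change little.

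It is also fair that 61% retention is near the planning floor: the sponsor expects at least 60 and better compliance with the new formulation. And the SAP adds two useful things that the protocol lacks, a week-104 limit and a rule for patients with no post-baseline SF. Simply reinstating the protocol text would lose them.

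**Conclusion.** The point holds as one of interpretation and consistency. As planned, the time-to-response curve and median describe response in the absence of discontinuation, while the primary treats discontinuation as failure, and nothing in either document tells the reader so. The modelled gap runs from about half the 9.6-point half-width planned for deferasirox, at light dropout, to about twice that half-width near the planning floor.

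These sizes rest on a constant response hazard, independent dropout and assumed dropout after month 12. Losses falling mainly after response would shrink the gap. In the other direction, the expected 60 is a follow-up figure: patients who stop treatment may stay in ocular follow-up, so discontinuation from treatment could exceed the loss to follow-up.

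The unranked censoring dates, the missing quartiles and the silence of SAP section 4 are real but minor discrepancies with the protocol. This should be corrected, but it does not threaten the primary analysis.

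**What to change.** 1. Add a cumulative incidence curve of response for each arm, with its median and quartiles, treating discontinuation or death before response as a competing event. Code patients with no post-baseline SF to match the primary's non-responder rule, and carry non-responding completers to the month-24 horizon. An SF ≤ 100 µg/L first seen after discontinuation should be handled as in the primary. The month-24 value then equals the primary rate.
2. Keep the protocol's Kaplan-Meier analysis alongside, labelled as response in the absence of discontinuation.
3. For Kaplan-Meier, state one rule: censor at the earliest of death, discontinuation, or last SF on or before week 104, and at the day of randomisation if there is no post-baseline SF. This keeps the SAP's two additions.
4. Restore the 25th and 75th percentiles with their confidence intervals.
5. Record any remaining departure from protocol 10.5.2 in SAP section 4.

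The cost is SAP wording and one extra standard output, with no new data. The added curve will look less favourable than Kaplan-Meier alone.
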